11. DEFINITION OF STUDY TIME POINTS

11.1. Definition of Diagnosis Date

Enrollment is the date on which the patient was diagnosed with the Fabry disease. For analysis of assessments which were not collected on the diagnosis date, the assessment closest to the diagnosis date will be utilized. If there are 2 assessments that are equidistant from the diagnosis date, then the assessment prior to diagnosis will be utilized.

11.2. Definition of the Migalastat or ERT Treatment Start or Treatment Switch

For analysis, if assessments were not collected on the treatment start date or a treatment switch date, then the assessment closest to the treatment start date will be utilized. If there are 2 assessments that are equidistant from the treatment start date, then the assessment prior to treatment start date will be utilized. Only assessments performed on that treatment will be used.

Treatment start date is used as the Analysis Start Date for comparing migalastat and ERT-treated patients. Diagnosis date is used as the Analysis Start Date for comparing migalastat and untreated patients.

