6.2. Missing Assessments

All data will be listed as collected. Descriptive statistics will be calculated on the data collected without replacement. For time to event, analysis data will be censored.

Missing and partial dates will be replaced as described in Section [6.1](#).

While it is possible that some patients will have missing or partial date information for SAEs or other safety data collections, analyses of the safety endpoints will include all patients in the Safety Population, unless specifically stated otherwise.

Missing data might be present for the analyses of the clinical laboratories and vital signs (eg, where the parameter was not measured at a required time points, which are the dates of treatment switch), and PROs. In many situations, there will often be other measurements of the parameter within a time frame that is applicable eg. during each treatment period. In such cases, the closest measurement to the switch time point within the treatment period will be used for analysis (Section 11). If such a measurement does not exist, then the patient will be excluded from the analysis of that variable at that timepoint. If 2 measurements are equidistant from the scheduled time point, the first one will be used.

Estimated GFR and LVMi data will be used as is and the actual time of the measurement will be utilized in the analysis. Analysis of LVMi will be exploratory.

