13.1.1. Cox Proportional Analysis for Fabry-associated Clinical Events

The time to the first event is defined as time from the Analysis Start Date to the first composite FACE (primary interest), and to the first cardiac, cerebrovascular, renal clinical event, or death due to FACEs. For the primary analysis, patients who complete the study without an event, are lost to follow-up, discontinued the study, started dialysis, had a kidney or heart transplant, or after 30 days they changed/switched therapy (migalastat group) or after they start therapy (untreated group) will be censored. Describing effectiveness in migalastat treated population is of the main interest.

Treatment Switch

The primary analysis will address events that occur on therapy from the Analysis Start Date up until 30 days after the patient stops therapy or switches therapy. The events that happen afterwards will be excluded. For the patients untreated at time of diagnosis, the primary analysis will address events from the time of diagnosis until the patient starts a therapy. The events that happen afterwards will be excluded. An additional analysis will be performed:

1. An analysis that will address events that occur on therapy from the time of Analysis Start Date up until the patient stops therapy or patient switches therapy. For the untreated patients, the analysis will address assessments from the time of diagnosis until the patient starts a therapy. The events that happen afterwards will be excluded.

Primary Analysis Method

The ratio of the hazards of treatment groups will be checked to ensure that the hazard ratios are constant over time. Secondly, the assumption that each variable in the model makes a linear contribution will be checked.

The covariates will include:

- sex
- age at the Analysis Start Date as a continuous variable
- eGFR_{CKD-EPI} at the Analysis Start Date as a continuous variable
- LVMi at the Analysis Start Date
- previous history of cardiac, cerebrovascular, and renal clinical events (composite event) as related to Analysis Start Date
- Length of treatment for Fabry disease

If the measurements are not available, measurements prior to and closest to the Analysis Start Date will be used. In case that more than 50% of values are missing for a given covariate, it will be dropped from the analysis.

The estimate of hazard ratio for migalastat-treated/untreated along with the associated 95% CI will be calculated.

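### SAP 11.2 contradicts itself on the treatment-start baseline and, read with 6.2, gives a post-start value whenever no assessment falls on the start date

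*SAP*

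**What the plan says.** SAP 11.2 sets the value that represents a patient at treatment start or switch. An assessment on the date itself comes first. If there is none, the closest one is taken, with a tie rule: "If there are 2 assessments that are equidistant from the treatment start date, then the assessment prior to treatment start date will be utilized". The paragraph ends: "Only assessments performed on that treatment will be used".

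SAP 6.2 treats switch dates as required time points. When a laboratory value, vital sign or PRO is missing there, "the closest measurement to the switch time point within the treatment period will be used for analysis". It continues: "If such a measurement does not exist, then the patient will be excluded from the analysis of that variable at that timepoint". It has its own tie rule: "If 2 measurements are equidistant from the scheduled time point, the first one will be used".

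Two other places look backwards in time. In SAP 13.1.1, covariates are taken at the Analysis Start Date, and if they are not available, "measurements prior to and closest to the Analysis Start Date will be used". SAP 13.7 repeats that fallback. The protocol (Treatments, Study treatment) wants switchers grouped, where possible, from a new baseline taken before the switch. SAP 17.1 declares no changes from the protocol.

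**The concern.** A baseline for measuring change under a treatment should precede that treatment. If it is taken while the patient is already on the drug, whatever has happened by then is subtracted from the reported change.

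The clearest case is in the documents themselves. The protocol's rationale says migalastat works by raising the patient's own α-Gal A activity, and SAP 14 summarises change in that activity from a start that may be treatment start. A baseline measured on migalastat already contains part of what is being measured.

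There is also a selection problem. Under 6.2, a patient with only a pre-start value drops out of the analysis of that variable at that time point. Whether a patient has a usable baseline then depends on staying on treatment until the next visit, which is itself a post-baseline outcome.

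**Working it through.** The plan gives no figure to reproduce. The check is a comparison of the rules, followed by simple timing arithmetic.

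**1. Does the last sentence of 11.2 void the tie-break?** A tie between assessments on different days needs one before the start and one after. At a first treatment start, the earlier one was made off treatment, so the last sentence excludes it. The later one is then the only candidate, and the tie-break cannot operate. At a switch, it is not stated whether the treatment meant is the outgoing or the incoming one.

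**2. Does 6.2 agree?** Its clause keeps the value inside the treatment period, which supports the restriction. Within one period all measurements lie on the same side of the switch date. Its tie rule therefore also has nothing to decide unless two values share a day.

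**3. Does 13.1.1 repair it?** Its condition can be read in two ways:
- No value on the Analysis Start Date: the covariate is then a pre-start value.
- No value after 11.2 has been applied: an on-treatment value is then used first.

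No text sets the order.

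**4. How late is an on-treatment baseline?**
- Input: visits every T = 12 or 24 months (Protocol, Method).
- Assumption: start falls uniformly between two visits, with no visit on the start date.
- Time to the first on-treatment visit: mean T/2, which is 12/2 = 6 or 24/2 = 12 months; maximum T, which is 12 or 24 months.
- Closest visit without the restriction: pre-start in half of cases; mean distance T/4 = 3 or 6 months; mean signed offset about 0.
- Last visit before start: on average T/2 = 6 or 12 months before it.

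The restriction therefore turns a rule with no average offset into one that is late by 6 to 12 months on average.

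**5. How much effect is already in the baseline?** The documents give no response speed. As an illustration only, assume an exponential approach to full effect with half-time h. The average share already present is 1 − [h/(T ln 2)] × [1 − 0.5^(T/h)]. For T = 12 and h = 6: 1 − (6/8.318) × 0.75 = 0.46.

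| Assumed half-time | Yearly visits | Two-yearly visits |
|---|---|---|
| 3 months | 66% | 82% |
| 6 months | 46% | 66% |
| 12 months | 28% | 46% |

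**6. Which analyses use this baseline?** In 11.2, treatment start is the Analysis Start Date for migalastat against ERT, and diagnosis is the start for migalastat against untreated.
- Exposed: descriptive changes from treatment start and per-switch summaries (13.7, 14, 15.6, and echocardiography through 15.10), and shift tables for laboratory and exploratory organ measures (15.6, 16.1 to 16.5).
- Possibly exposed, for migalastat against ERT: the eGFR and LVMi Cox covariates (13.1.1), the eGFR subgroups (12), and the reference creatinine for the doubling event (3.1).
- Largely unaffected: the primary comparison started at diagnosis, the MMRM for eGFR (its covariates are enrollment values), the individual eGFR slopes (6.2 uses actual measurement times), and descriptive PRO change, which 16.9 runs from diagnosis.

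**The case against.** The strongest reply is that the SAP does not settle on a post-exposure baseline. A start-date assessment comes first and need not follow the first dose. The tie-break, the 13.1.1 fallback and the protocol all favour a pre-start value. This stands: a reader might infer that baseline must always be post-exposure, and the documents do not support that. They support a contradiction whose literal resolution is post-start when the start date has no assessment.

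Second, the natural reading of 13.1.1 may be that unavailable means not available on that date, so the Cox covariates would be pre-start. This also stands as far as it goes. The covariates are only possibly affected, and the order of the two rules needs stating.

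Third, 6.2 does not define baseline. A switch date is also the end point of a change from the Analysis Start Date, and there the within-period clause properly keeps out values from another therapy. This is right, and it is a reason not to delete the clause outright.

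Fourth, a reader might infer that the reported change would be only a small remainder of the true one. That needs a fast response, and the protocol describes very slow disease progression. One curve cannot be assumed for enzyme activity, LVMi and albuminuria alike. With a 12-month half-time and yearly visits the share is 28%. The direction of the loss for an early response stands; its size is not established.

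**Conclusion.** The point holds as an internal contradiction with a practical consequence. Taken literally, the last sentence of 11.2 cancels its own tie-break. With 6.2 it gives a post-start baseline to patients without a start-date assessment, contrary to the protocol's pre-switch baseline and to the direction of the 13.1.1 fallback.

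For those patients the delay averages 6 to 12 months and is at most 12 to 24, given the stated visit spacing and starts assumed uniform between visits. Part of any early effect is then lost from the change. The shares of 28% to 82% rest on assumed half-times of 3 to 12 months and only illustrate the dependence on response speed.

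A reader might go further and conclude that the primary result is biased by this rule. The documents do not support that, because 11.2 starts the migalastat-untreated comparison at diagnosis. SAP 3.1 describes the primary endpoint as running from treatment start for migalastat, so the limit applies to the comparison as 11.2 starts it. The correction should be made before analysis, because the SAP as written lets two programmers derive different baselines.

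**What to change.** - In 11.2, define the treatment-start or switch baseline as the last assessment on or before the start or switch date, within a look-back that covers the visit interval (about 24 months). Report the age of the value used. A 12-month look-back is too short: with two-yearly visits and uniform starts, 12/24 = 50% of starts would have no visit inside it.
- Use an early post-start value only if no earlier one exists, and flag it.
- Keep the on-treatment sentence in 11.2 and the within-period clause in 6.2, but limit both to post-baseline and end-of-period values, so that a change ending at a switch does not pick up a value from another therapy.
- State in 13.1.1 and 13.7 that the fallback follows the same baseline definition, and that the eGFR subgroups and the reference creatinine use it too.

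The cost is SAP wording only. The downside is that some baselines will be older. Under the same timing assumption, the last value before start is on average 6 months old with yearly visits and 12 months old with two-yearly visits.

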3. STUDY ENDPOINTS

3.1. Primary Effectiveness Analysis

The primary endpoint is time to first FACE (cardiac, renal, or cerebrovascular events) ") since start of treatment for migalastat and or ERT and from time of diagnosis for untreated with particular focus on the added value of the recent addition of migalastat as a treatment option. A formal statistical analysis will be using the initial treatment cohort. Descriptive statistics will be calculated since each start of treatment (after each switch).

FACEs are defined as the following:

- Cardiac clinical events:
 - Myocardial infarction
 - New symptomatic arrhythmia requiring medication, direct current cardioversion, or interventional procedure (e.g., ablation, pacemaker, or defibrillator implantation)
 - Unstable angina defined by national practice guidelines and accompanied by electrocardiographic changes and non-ST segment elevation myocardial infarction [UA/NSTEMI]) and accompanied by electrocardiographic changes
 - Congestive heart failure requiring hospitalization
 - Any major cardiac medical procedure (e.g., valve replacement, stent-implantation, transplant, or persistent atrial fibrillation)
- Cerebrovascular clinical events:
 - Stroke (documented by a physician)
 - Transient ischemic attack (documented by a physician)
- Renal clinical events
 - Doubling of serum creatinine level from the start of analysis (2 consecutive values)
 - End-stage renal disease (ESRD) requiring long-term dialysis or transplantation
- Death due to FACEs

All FACEs will be analyzed together as a composite and separately in each category (cardiac, cerebrovascular, and renal). Death due to FACE will be analyzed under the category in which it occurred (cardiac, cerebrovascular, or renal).

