5.2. Effectiveness Populations

5.2.1. Primary Effectiveness Population

The Primary-Effectiveness Population is defined as subsets of the migalastat-treated group, the untreated group, and ERT-treated group as comparators.

Patients who enter the study as untreated but switch to a treatment (migalastat or ERT) within 3 months from enrollment will be considered in analysis as initially belonging to a treatment group they switched to. Depending on an analysis as further discussed the group assignment might change in the case of a treatment switch.

All data collected will be utilized to establish the Primary Effectiveness Population for the analysis. Patients need to have a documented amenable variant to be included in the Primary Effectiveness Population and must meet criteria for receiving treatment for migalastat.

All patients from the Danish National Fabry Centre will be included, estimating the inclusion of 115 individuals (sex ratio [female:male] – 2:1). Pre-specified subgroups include: non-amenable/ amenable to migalastat, males/females.

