9.1. Demographics

Demographic variables collected prior to enrollment include date of birth, sex, race, and ethnicity. Age at baseline date of diagnosis for untreated patients and the date of start of the first treatment for treated patients), sex, race, ethnicity, pregnancy status for female patients and fertility status for male patients, will be summarized and reported.

For the Safety Population, data will be summarized at the time of diagnosis.

Age at the time of diagnosis (migalastat-treated versus untreated patients) and age at the start of the first treatment (migalastat-treated versus ERT-treated patients) will be analyzed as a continuous variable and will also be compared between groups using the categories: (< 12, 12 to < 18, 18 to < 65, \geq 65). Sex, ethnicity, and race will be analyzed as categorical variables.

Patient height and weight will be analyzed at the time of diagnosis and at the treatment start. Height and weight will be reported in metric units (height in cm and weight in kg) and will be analyzed as continuous variables.

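### SAP 3.1 and 11.2 give the migalastat group different time origins in the primary migalastat-versus-untreated comparison, and 13.1.1 does not say who is in that group

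*SAP*

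**What the plan says.** - **SAP 3.1** measures time to first FACE "since start of treatment for migalastat and or ERT and from time of diagnosis for untreated". It adds: "A formal statistical analysis will be using the initial treatment cohort". Periods after each switch receive descriptive statistics only.
- **SAP 5.2.1** describes the primary population as "defined as subsets of the migalastat-treated group, the untreated group, and ERT-treated group as comparators", restricted to amenable variants. Patients who enter untreated but start migalastat or ERT "within 3 months from enrollment will be considered in analysis as initially belonging to a treatment group they switched to". The next sentence loosens this: "Depending on an analysis as further discussed the group assignment might change in the case of a treatment switch". Under SAP 11.1, enrollment is the diagnosis date.
- **SAP 9.1** sets baseline at "the date of start of the first treatment for treated patients", yet takes age at diagnosis for the comparison with untreated patients.
- **SAP 11.2** states: "Diagnosis date is used as the Analysis Start Date for comparing migalastat and untreated patients". Treatment start is kept for migalastat versus ERT. SAP 12 repeats this split.
- **SAP 13.1.1** runs time from the Analysis Start Date, so it takes the 11.2 origin. It counts on-therapy events up to 30 days after stop or switch, and follows patients untreated at diagnosis until they start a therapy. It mentions neither the initial cohort nor the 3-month window. Its covariates include the length of Fabry treatment, with no time point at which this is measured.

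**The concern.** This is the test that SAP 3.2 and 13.1 name as primary, at the two-sided 0.05 level. Its time zero has two definitions, and the section that specifies the model does not say which patients form the migalastat arm.

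The two gaps interact. With a diagnosis origin and on-therapy events only, time between diagnosis and migalastat start is counted at risk although no event in it can count for migalastat (immortal time). How much of it there is depends on the group rule: at most 3 months if the initial cohort is used, possibly many years if later starters are admitted.

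The treatment-length covariate raises a related question. SAP 2 says that all patients are treatment-naïve at diagnosis, so at that origin the value is zero for everyone. If it varies, it may be duration accrued after baseline.

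**Working it through.** The SAP states no event rate, effect size or arm size (SAP 4), so there is no figure to reproduce. All results below assume no treatment effect.

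**Inputs from the documents:** 115 patients; follow-up from 2001 to the end of 2022 (protocol) or 2023 (SAP 2); migalastat available from 2016; 3-month window.

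**Assumptions:** diagnoses uniform over 22 years; half of patients start migalastat, none before mid-2016; delay to start exponential with mean 0.25 to 1 year; 20 to 50 FACEs per 1000 person-years.

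**1. Size of the migalastat arm, initial cohort.**
- Diagnosed since mid-2016: 115 × 6.5/22 = 34. Half start: 17.
- Start within 3 months, mean delay 1 year: 17 × (1 − exp(−0.25/1)) = 17 × 0.22 = 3.8.
- Mean delay 0.25 year: 17 × (1 − exp(−0.25/0.25)) = 17 × 0.63 = 10.7.
- If only 30% were amenable, the low end is 34 × 0.3 × 0.5 × 0.22 = 1.1. A mean delay of 0.1 year would give 17 × 0.92 = 15.6.
- With about 3.27 years on therapy each, expected events are at most 3.8 × 3.27 × 0.02 = 0.25 to 10.7 × 3.27 × 0.05 = 1.75.
- With 2 migalastat events, the 95% interval extends by a factor of at least exp(1.96 × √(1/2)) = 4.0 each way.

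**2. Origin bias, initial cohort.** Under constant risk, the null ratio is on-therapy time divided by time since diagnosis.
- Mean gap 0.12 year: 3.27/3.39 = 0.96.
- Every starter using the full window: 3.2/3.45 = 0.93.
- Large null Cox simulations, relative to delayed entry: 0.96 to 1.00 for the 11.2 origin. For the 3.1 origin, 1.00, rising to 1.06 when risk rises with time since diagnosis (Weibull shape 2).

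**3. Later starters admitted, 11.2 origin, on-therapy events only.** The null ratio for one patient is 1 − (pre-migalastat years / total years).
- Diagnosed at the start of 2001, migalastat from the start of 2016, followed to the end of 2022: 1 − 15/22 = 0.32. To the end of 2023: 1 − 15/23 = 0.35.
- Diagnosed 2011: 1 − 5/12 = 0.58.
- Null Cox simulations over delays of 0.1 to 3 years and 0 to 50% taking ERT first gave 0.29 to 0.60 unadjusted and 0.25 to 0.57 adjusted for age. For example, at 30 per 1000 person-years, 1-year delay and no ERT, the ratio was 0.39, against 1.02 with delayed entry. Another set-up, without ERT and with half of patients starting at some time from 2016, gave 0.22 to 0.44.
- The 3.1 origin is no remedy for later starters. In that second set-up it gave 0.98 to 1.01 at constant risk but 1.9 to 2.0 when risk rose with time since diagnosis (Weibull shape 1.5), because migalastat patients are then matched to untreated patients nearer to diagnosis.

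**4. Treatment length.**
- Measured at the diagnosis origin: zero for all, so the term drops out.
- Realised length cut off at the FACE: null hazard ratio about 7 to 23 across initial-cohort simulations.
- Realised length to data cut-off: 0.93 to 1.09, against 0.92 to 1.10 without the covariate; runs with few events scattered from 0.6 to 1.7.

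**The case against.** Much of the text points to the benign reading. SAP 3.1 ties the formal analysis to the initial cohort. SAP 13.1.1 censors untreated patients when they start therapy and gives later treatment periods descriptive statistics only, so later starters already have a place. The sentence allowing assignment to change is limited to analyses discussed further on, and such changes appear in 13.1.2, 13.3 and 15.1, not in the formal test of 13.1.1. The wording about subsets is followed by an amenability restriction, not a timing rule. SAP 9.1 concerns demographic tables. SAP 13.1.2 already plans time-dependent exposure.

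Most of this stands, and it rules out two stronger inferences. A reader might infer that the plan commits the primary test to years of immortal time. In simulations of that reading, 4 to 77% of null trials with 35 to 80 patients showed a significant protective result. The documents do not support this as the declared analysis: it needs a group rule that they leave open but do not favour.

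A reader might also infer that the treatment-length covariate must wreck the hazard ratio. It need not. SAP 6.1 and 10 use treatment duration before enrollment, which gives a meaning free of future information, though one at odds with patients being untreated at diagnosis. A value of zero for all is harmless. The extreme ratios arise when realised length is cut off at the FACE.

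The objection does not remove the two origins for one test, nor the missing group definition. Read literally, the 13.1.1 rule for patients untreated at diagnosis covers everyone, including those whom 5.2.1 moves to migalastat. SAP 13.1.2 is not the primary analysis. Its worked example also needs correction: it places an event at Month 24, untreated, for a patient who dies at Month 26 on ERT.

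**Conclusion.** The conflict between 3.1 and 11.2 and the silence of 13.1.1 are plain on the page and do not depend on any assumption. They should be settled before the primary analysis is run.

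The numerical consequence depends on the reading. Under the favoured one, immortal time is at most 3 months and the null hazard ratio is about 0.93 to 1.06, which is small beside the imprecision of an arm of perhaps 4 to 11 patients. If later starters are admitted with the 11.2 origin and on-therapy events only, the null ratio is illustratively 0.3 to 0.6. That small arm matters: SAP 13.1 defers the test until data suffice but gives no threshold, so there could be pressure to widen the group.

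Arm size, event rates, uptake and delays are assumed throughout. The direction of the later-starter bias follows from the counting rule; its size does not transfer beyond these assumptions.

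**What to change.** 1. State one time origin and one migalastat-group rule, in the same words, in SAP 3.1, 5.2.1, 9.1, 11.2, 12 and 13.1.1.
2. Credit no pre-migalastat time to migalastat. If the initial cohort is meant, write that rule into 13.1.1 and use delayed entry or a 3-month landmark (mean null hazard ratio 1.00 in simulation; the two agree within 1%). If later starters are meant, use time since diagnosis, count time up to first therapy as untreated, and let patients enter the migalastat risk set at migalastat start (null hazard ratio 0.94 to 1.06).
3. State how a FACE that occurs before migalastat start is handled.
4. Define the treatment-length covariate as treatment received before entry to the interval. At a diagnosis origin it is then zero for all and can be dropped. Do not use duration realised after baseline.

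The cost is SAP wording and risk-set programming. Diagnosis, treatment start, switch and FACE dates are already collected. The migalastat estimate may become less favourable or less precise, and with the initial cohort there may be too few migalastat events for a formal test.
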